#### 4. PLANNED ANALYSES

The following analyses will be performed for this study:

Final Analysis

# 4.1. DATA MONITORING COMMITTEE (DMC)

There will be no DMC for this study.

#### 4.2. FINAL ANALYSIS

All final, planned analyses identified in this SAP will be performed by IQVIA Biostatistics following Sponsor Authorization of this Statistical Analysis Plan, Database Lock, Sponsor Authorization of Analysis Populations.

Document: \\ieedc-vnasc01\BIOSdata\Menarini\NebZof\KZA41200\Biostatistics\Documentation\SAP

Author: [name] Version Number: Final V1.0

Version Date: [14Dec2021]

Template No.: CS\_TP\_BS016 Revision 6 Reference: CS\_WI\_BS005

Page 17 of 37

### 5. ANALYSIS POPULATION

Agreement and authorization of patients included/excluded from each analysis population will be conducted prior to database lock of the study. A data review meeting will be conducted prior to database lock and confirm the patients in each analysis set population. Impact of Covid-19 pandemic on the missed data, missed visits or dropouts will be assessed during this meeting and appropriate decisions on population counts will be taken.

# 5.1. ENROLLED [ENR] POPULATION

The enrolled (ENR) population will contain all patients who are enrolled into the study and may or may not receive the study drug (extemporaneous combination)

# **5.2.** Intent-to-treat [ITT] Population

The intent-to-treat (ITT) population will contain all patients in the ENR population and receive at least 1 dose of study drug (combination therapy) and have at least 1 post baseline safety assessment

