### 7.1 Procedures and Study Visits

Patients will attend a total of 3 visits during the study. The description of the activities, procedures and tests to be performed at each visit is detailed below:

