#### **Protocol Template**

Sponsor: Menarini Pharmaceutical Study Code: MEIN/19/ZoNe-HYP/001

Protocol Version\_1 of 16/07/2020

- Enrolled population: Patients who are enrolled into the study and may or may not receive the study drug (extemporaneous combination)
- Intent-to-Treat population: Patients who are in the Enrolled population and receive at least 1 dose of study drug (combination therapy) and have at least 1 post baseline safety assessment
- Safety population: Patients who are in the Enrolled population and receive at least
   1 dose of study drug (combination therapy)
- Per protocol population: All patients included in the safety population who do not have any major protocol deviations will be included in this population

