#### 14.5.9 Data Imputations

As a part of missing data analysis Multiple Imputation (MI) simulation method for imputing missing data will be conducted on the primary efficacy endpoint using ITT population. This will help to assess the impact of missing data on the primary analysis.

The SAS procedure MI will be used, and the details of MI procedure will be stated in the dataset specification document. If the data is monotone missing, an imputation model with regression baseline parameters (age, gender, country/site, monotherapy and baseline values) will be applied, otherwise Markov Chain Monte Carlo (MCMC) will be applied. All variables included in the analysis model and values at Week 0 for the primary endpoint will be included in the imputation model. To reduce the sampling variability from the imputation process, 50 datasets will be generated.

In the estimation step, separate analysis will be performed using the paired t-test.

After the completion of the estimation step SAS procedure MIANALYZE will be used to pool the estimates.

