# 5.3. SAFETY [SAF] POPULATION

The safety (SAF) population will contain all patients who are in the ENR population and receive at least 1 dose of study drug (combination therapy)

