### 6. GENERAL CONSIDERATIONS

### **6.1.** REFERENCE START DATE AND STUDY DAY

Study Day will be calculated from the reference start date and will be used to show start/stop day of assessments and events. Reference start date is defined as the day of the first dose of study drug (combination therapy) (Visit 2), (Day 1 is the day of the first dose of study drug ) and will appear in every listing where an assessment date or event date appears.

- If the date of the event is on or after the reference date, then:
- Study Day = (date of event reference date) + 1. If the date of the event is prior to the reference date, then: Study Day = (date of event – reference date).

In the situation where the event date is partial or missing, Study Day, and any corresponding durations will appear partial or missing in the listings.

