#### 7. STATISTICAL CONSIDERATIONS

Summaries will include descriptive statistics for continuous variables (sample size [n], mean, standard deviation [SD], median, minimum and maximum) and for categorical variables (frequency [n] and percentage), unless otherwise stated in the relevant section. Percentages will be based on the number of patients within the relevant analysis population and treatment arm, or the number of patients with data available where relevant.

If the original data has N decimal places, then the summary statistics will have the following decimal places:

Minimum and maximum: N

Mean, median, Q1, Q3, confidence intervals, ratios: N + 1

SD: N+2

Percentages will be reported to one decimal place. P-values should be reported to three decimal places, except values <1.000 but >0.999 will be presented as '>0.999' (e.g., 0.9998 is presented as >0.999); and values <0.001 will be presented as '<0.001' (e.g., 0.0009 is presented as <0.001)

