#### 16.2.2. ANALYSIS OF SECONDARY EFFICACY VARIABLES

Secondary efficacy variables will be summarized in a descriptive manner using ITT population.

• Change in mean sitting SBP between Week 0 (Visit 2) and Week 8 (Visit 3):

Change from baseline in sitting SBP from prior and post combination therapy will be compared using paired t-test. The p-value will be presented using a paired t-test comparing mean at baseline and mean at Week 8. The secondary endpoint will be presented in a descriptive manner using n, mean, median, SD, Q1, Q3, and minimum and maximum.

Assumption of normality will be investigated using Wilk-Shapiro test. If violation is observed, then paired t-test will be replaced by Wilcoxon signed rank test.

• The number of patients achieving BP goal (sitting BP ≤130/80 mmHg) will be summarized for Visit 2 and Visit 3, along with percentage. A p-value using exact McNemar's test will be presented to compare the proportion of patients achieving the BP goal (sitting BP ≤130/80 mmHg) between Visit 2 and Visit 3.

Document: \\ieedc-vnasc01\BIOSdata\Menarini\NebZof\KZA41200\Biostatistics\Documentation\SAP

Author: [name] Version Number: Final V1.0

Version Date: [14Dec2021]

Template No.: CS\_TP\_BS016 Revision 6 Reference: CS\_WI\_BS005

Page 27 of 37

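### Treated patients lost without contact before Week 8 fall out of the ITT set, and no rule says how patients without a Week 8 reading count in the blood pressure goal rate

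*SAP*

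**What the plan says.** SAP 5.2 places in ITT those enrolled patients who "receive at least 1 dose of study drug (combination therapy) and have at least 1 post baseline safety assessment". Protocol 14.3 has the same second condition: "and have at least 1 post baseline safety assessment". The safety set (SAP 5.3) needs only the combination dose, so ITT is the safety set minus treated patients with no post-baseline safety assessment. Neither document defines a safety assessment for this purpose.

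Protocol 7.1 states: "Patients will attend a total of 3 visits during the study". They fall at Weeks −4, 0 and 8. SAP 6.2 takes baseline before the first combination dose. Protocol 7 and the note to Table 9.1 put the dose after the assessments on visit days.

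For the goal rate, SAP 16.2.2 says: "Secondary efficacy variables will be summarized in a descriptive manner using ITT population". SAP 7.3 rules out imputation of missing efficacy data. On denominators, SAP 7 says: "Percentages will be based on the number of patients within the relevant analysis population and treatment arm, or the number of patients with data available", the latter where relevant, and nothing chooses between the two for the goal rate.

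**The concern.** A set labelled ITT should not depend on whether the patient came back for the outcome visit. Here the one scheduled visit that can meet the entry condition is also the visit that measures every efficacy endpoint. A patient who takes the combination and then disappears is out of ITT, and no later step restores that patient to the Week 8 goal rate.

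The goal rate is secondary estimand 2 in SAP 2.4, and Protocol 6 presents it as an important indicator of therapeutic success. SAP 3.3 notes that the Visit 2 rate is always zero, so the Week 8 percentage is the whole result, and the study has no concurrent control against which to judge attrition. If patients tend to disappear because the combination does not work or does not suit them, the reported percentage is too high.

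**Working it through.** **Which assessments can satisfy the condition.** Visit 2 measurements precede the first combination dose, so they are baseline. The flow charts (Protocol 4.1, SAP 3.2) list nothing between Week 0 and Week 8. That leaves Visit 3, or an unscheduled contact.

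**Which patients are affected.**
- Lost without contact: Protocol 13 defines this as not returning and not being reachable. Such a patient has no later assessment, so is out of ITT and in the safety set.
- Early discontinuers: Protocol 12 asks them to complete the Visit 3 assessments and requires follow-up of patients withdrawn for an adverse event. They can qualify for ITT. A reading before Day 53 is outside the Visit 3 window of Days 53 to 59 (SAP 6.4), and SAP 6.3 mentions early discontinuation data only for listings.
- Remote reports: Protocol 11.9 collects adverse events reported by phone, letter or email. Whether such a report is a safety assessment is not stated.

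**The plan's own figures.** The 216 patients size the DBP endpoint. A one-sample t-test with net difference 4 − 2 = 2 mmHg, SD 10 and one-sided 5% gives n = 216 and power 90.1%. For the number screened, 216/(1 − 0.25) = 288, against 290 stated. Neither figure gives an expected goal rate or a Visit 2 to Visit 3 loss. Protocol 14.2 includes screen failure in the 25%, which runs from Visit 1 to Visit 3.

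**Size of the effect.** Let r be the goal rate among patients with a Week 8 reading and d the proportion of treated patients without one. Counting those as not at goal:
- all-treated rate = r × (1 − d)
- ratio of the attender rate to the all-treated rate = 1/(1 − d)
- difference = r × d

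Assumptions: 220 patients start the combination (the cap of 110 per drug, Protocol 7) and r is about 40%. The lowest d is (220 − 216)/220 = 1.8%, from the cap and the planned completers. The highest puts the whole 25% allowance after Visit 2.

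| d | Lost | With Week 8 reading | At goal | Rate, attenders | Rate, all treated | Difference (points) |
|---|---|---|---|---|---|---|
| 1.8% | 4 | 216 | 86 | 39.8% | 39.1% | 0.7 |
| 5% | 11 | 209 | 84 | 40.2% | 38.2% | 2.0 |
| 10% | 22 | 198 | 79 | 39.9% | 35.9% | 4.0 |
| 15% | 33 | 187 | 75 | 40.1% | 34.1% | 6.0 |
| 25% | 55 | 165 | 66 | 40.0% | 30.0% | 10.0 |

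For r between 20% and 60%, the difference is 0.4 to 1.1 points at 1.8% loss, 2 to 6 at 10%, and 5 to 15 at 25%.

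**Effect on the tests.** A patient without a Week 8 DBP contributes no pair to the observed-case t-test under either ITT definition. With no patient at goal at Visit 2, the exact McNemar p-value is 2 × 0.5^k for k patients at goal at Week 8 (k = 5: 0.0625; k = 6: 0.031). Added patients not at goal are concordant pairs and leave it unchanged.

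**The case against.** The strongest reply is that the documents already cover much of this. Patients known to have withdrawn are asked back for the Visit 3 assessments, and those leaving for an adverse event are followed, so a reader who infers that ITT is simply the set of Visit 3 attenders, or that everyone leaving for intolerance is removed by definition, goes too far. That stands: exclusion is certain only for patients lost without contact.

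A reader might also infer that the SAP computes the goal rate on attenders, or that the loss is hidden. Neither is supported. SAP 7 leaves the denominator open. SAP 9.1 reports reasons for exclusion from each population, the safety set counts everyone dosed, and the primary result gives n. But disclosure does not correct the percentage. SAP 16.3.2 does name the safety population for exploratory goal summaries, but the variables in SAP 16.3.1 split patients by prior therapy or subgroup, and no rule covers a missing Week 8 reading there either.

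Protocol 14.5.9 planned multiple imputation, with "imputing missing data will be conducted on the primary efficacy endpoint using ITT population". SAP 3.3 withdrew it. Even if kept, it would not have reached patients already outside ITT.

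Counting missing as not at goal is also only one convention. If all the lost patients had in fact reached goal, the all-treated rate would be (86 + 4)/220 = 40.9% at 1.8% loss and (79 + 22)/220 = 45.9% at 10%. That stands too, and is a reason to keep the observed-case rate alongside.

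**Conclusion.** The concern holds for treated patients lost without contact: they leave ITT, stay in the safety set, and nothing returns them to the Week 8 goal rate. For early discontinuers the defect is a missing rule rather than certain exclusion.

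With 40% of attenders at goal and missing counted as not at goal, the reported rate would exceed the all-treated rate by about 0.7 points at 1.8% loss, 4 at 10% and 10 at 25%. The goal rate and the loss are both assumptions. The 1.8% relies on Protocol 7, where 216 is the number completing; Protocol 14.2 describes 216 as entering the assessment period. The 25% is an upper bound because it also covers screen failures and run-in exits.

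A reader might infer that the primary result is compromised. The documents do not support that from this rule: the observed-case t-test and the exact McNemar p-value are identical under either definition. This does not show that the observed-case analysis is free of attrition bias, only that the ITT wording does not alter it. What is at stake is one secondary percentage and the accuracy of the ITT label.

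**What to change.** 1. In SAP 16.2.2, report the Week 8 goal rate with all patients who took at least one combination dose as denominator, counting those without a Week 8 reading as not at goal. Keep the observed-case rate as supportive. Add this exception to SAP 7.3, which otherwise forbids it.
2. In Protocol 14.3 and SAP 5.2, define ITT by the dose criterion alone, so that it equals the safety set. Check under Protocol 14.7 whether redefining the primary analysis set is a substantial amendment. If this step is not taken, step 1 can still go ahead by naming the safety set as the denominator in SAP 16.2.2 and in secondary estimand 2 (SAP 2.4).
3. Show the number of treated patients without a Week 8 DBP beside the primary result.

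No new data are needed. Steps 1 and 3 are SAP wording. The costs are a slightly lower reported goal rate and, for step 2, possible amendment work, including the ethics committee and authority approval that Protocol 14.6 requires for substantial amendments.

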# 5.3. SAFETY [SAF] POPULATION

The safety (SAF) population will contain all patients who are in the ENR population and receive at least 1 dose of study drug (combination therapy)

# 5.4. PER PROTOCOL [PP] POPULATION

The per-protocol (PP) population will contain all patients in the SAF population who have not experienced major protocol violations that could affect the efficacy analyses. Patients with major protocol deviations which can affect the primary endpoint of the study, failure to satisfy inclusion or exclusion criteria, taking any prohibited medications affecting blood pressure during the study, serious non-compliance to dose regimen and visit schedule are excluded. Whether to include or exclude the patients from PP set will be finalized in the data review meeting prior to database lock.

Document: \\ieedc-vnasc01\BIOSdata\Menarini\NebZof\KZA41200\Biostatistics\Documentation\SAP

Author: [name] Version Number: Final V1.0

Version Date: [14Dec2021]

Template No.: CS\_TP\_BS016 Revision 6 Reference: CS\_WI\_BS005

Page 18 of 37

### 6. GENERAL CONSIDERATIONS

### **6.1.** REFERENCE START DATE AND STUDY DAY

Study Day will be calculated from the reference start date and will be used to show start/stop day of assessments and events. Reference start date is defined as the day of the first dose of study drug (combination therapy) (Visit 2), (Day 1 is the day of the first dose of study drug ) and will appear in every listing where an assessment date or event date appears.

- If the date of the event is on or after the reference date, then:
- Study Day = (date of event reference date) + 1. If the date of the event is prior to the reference date, then: Study Day = (date of event – reference date).

In the situation where the event date is partial or missing, Study Day, and any corresponding durations will appear partial or missing in the listings.

#### **6.2.** BASELINE

Unless otherwise specified, baseline is defined as the last non-missing measurement taken same day or prior to reference start date (including unscheduled assessments) before first dose of study medication (combination therapy). Adverse Events (AEs) and medications commencing on the reference start date/time will be considered post-baseline, unless the start time of the AE is known to be prior to the first dosing of the study drug. Since there is no Lab assessment in Visit 2, Lab values collected at Visit 1 will be considered baseline for Lab data.

# 6.3. RETESTS, UNSCHEDULED VISITS AND EARLY TERMINATION DATA

In general, for by-visit summaries, data recorded at the nominal visit will be presented. Unscheduled measurements will not be included in by-visit summaries. Listings will include scheduled, unscheduled, retest and early discontinuation data.

Document: \\ieedc-vnasc01\BIOSdata\Menarini\NebZof\KZA41200\Biostatistics\Documentation\SAP

Author: [name] Version Number: Final V1.0

Version Date: [14Dec2021]

Template No.: CS\_TP\_BS016 Revision 6 Reference: CS\_WI\_BS005

Page 19 of 37

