## 10.2.4 Electrocardiograms

A single 12-lead resting ECG will be recorded after the patient has been supine for at least 5 minutes to calculate the heart rate and measure PR, QRS, QT, and QTc intervals. The results will be recorded in the eCRF. A trained clinical site physician will perform the clinical assessment of each 12-lead ECG. Additional 12-lead ECGs will be performed at other times if judged to be clinically appropriate or if the ongoing review of the data suggests a more detailed assessment of ECGs is required.

Identification Number: FORM-000050125

Previous Doc Number:
CTWI10A

Version Number: 1.0, CURRENT

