## Withdrawal of patient from the study

The patient may withdraw from the study at any time without explanation, without losing the right to future medical care. The participation of the patient may, at any moment, be terminated by the Investigator, if considered appropriate.

A patient can be withdrawn during the study for any of the following reasons:

- Any AE, which required treatment and study termination for the patient according to the Investigator's judgement
- Abnormal renal function or liver enzyme parameters as described in Section 10.2
- Patient becomes pregnant during the study
- Request of the patient (without giving any reason)
- Investigator deems it to be in the best interest of the patient to discontinue
- Failure to adequately comply with the dosing, evaluations, or other requirements of the study
- If the patient meets an exclusion criterion (newly developed or not previously recognized) that precludes further study participation
- Use of any prohibited medication (eg, concomitant use of aliskiren-containing products and ACE-i with sacubitril/valsartan or any other drug as specified per SmPCs of ZOF or NEB) that in the opinion of the Investigator or Sponsor necessitates the patient being withdrawn

The reason for the withdrawal of monotherapies or study drug, or withdrawal from the study must be well documented in the eCRF page and should capture the date and the specific underlying reason for discontinuation of study treatment or patient discontinuation/withdrawal.

Patients who discontinue from the study early will be asked, anyway, to complete all the assessments of Visit 3. Patients may discontinue the study product, but remain in the study for follow-up, especially for safety study endpoints (if applicable).

If a patient has been discontinued/withdrawn due to an AE, the Investigator must immediately notify the relevant pharmacovigilance contact (see Section 11.9) and should be followed-up until

Identification Number: FORM-000050125

Previous Doc Number:
CTWI10A

Version Number: 1.0, CURRENT

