#### **6.4.** WINDOWING CONVENTIONS

The following table describes assignment of visit windows for the purposes of analysis:

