#### 18.3. LABORATORY EVALUATIONS

Results from the central laboratory will be included in the reporting of this study for Hematology, Blood Chemistry and Pregnancy test. A list of laboratory assessments to be included in the outputs is included in protocol Section 10.2.3. Laboratory evaluations will be summarized for Combination therapy by SAF population. Presentations will use SI Units.

The following summaries will be provided for laboratory data:

Document: \\ieedc-vnasc01\BIOSdata\Menarini\NebZof\KZA41200\Biostatistics\Documentation\SAP

Author: [name] Version Number: Final V1.0

Version Date: [14Dec2021]

Template No.: CS\_TP\_BS016 Revision 6 Reference: CS\_WI\_BS005

Page 30 of 37

- A descriptive summary of lab parameters by visit.
- The Shift from screening (visit 1)according to the lab result summary will be provided for laboratory data
- A by-patient listing of all laboratory data and pregnancy test data will be presented.

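### SAP 6.3 leaves unscheduled on-combination values out of the by-visit safety summaries, no worst or last post-baseline summary is specified, and SAP 6.3 and 6.4 conflict for early leavers

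*SAP*

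**What the plan says.** SAP 6.3 opens with a general rule: "In general, for by-visit summaries, data recorded at the nominal visit will be presented". It then makes one explicit exclusion, and names retest and early-discontinuation data only in the sentence on listings: "Unscheduled measurements will not be included in by-visit summaries. Listings will include scheduled, unscheduled, retest and early discontinuation data".

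SAP 6.4 introduces Table A with "The following table describes assignment of visit windows for the purposes of analysis". The table gives Visit 2 Study Days -2 to 2 and Visit 3 Study Days 53 to 59. Nothing is assigned to the days between.

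Protocol section 12 says of early leavers: "Patients who discontinue from the study early will be asked, anyway, to complete all the assessments of Visit 3". Protocol 10.2.4 foresees ECGs outside the schedule: "Additional 12-lead ECGs will be performed at other times if judged to be clinically appropriate".

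The planned parameter outputs are in SAP 18.3 to 18.6. For laboratory data they are "A descriptive summary of lab parameters by visit" and a shift from screening. Vital-sign and examination outputs are also by visit, and the examination output includes a shift from baseline. ECG output is a descriptive summary; the protocol (14.5.7) makes it by visit, while the SAP does not repeat those words.

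**The concern.** Safety and tolerability of the combination is a secondary objective. The trial is open-label, has no concurrent control and has no data monitoring committee, so the safety summaries carry more weight than they would in a comparative trial. An unscheduled test is usually taken because something has raised concern. If such values are left out of the summaries, the parameter tables lean towards a safer picture than the collected data. For early leavers the problem is ambiguity: two programmers following the SAP could produce different Week 8 columns from the same data.

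**Working it through.** **1. Which on-combination values can be scheduled ones?** In the flow chart (protocol 4.1, SAP 3.2), ECG, vital signs and physical examination are done at Visits 1, 2 and 3, and laboratory tests at Visits 1 and 3 only. On visit days study medication is taken after the assessments, so Visit 2 precedes the first combination dose. Visit 3 is the only scheduled post-baseline point in every domain.

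Protocol 10.2.3 withdraws patients with stated renal or liver values. No laboratory test is scheduled on the combination before Visit 3, so an on-combination result that triggers this rule earlier must come from an unscheduled test. The 6.3 exclusion applies to that result. It applies equally to an extra ECG under protocol 10.2.4, if the ECG summary is by visit as the protocol says.

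SAP 6.2, by contrast, accepts unscheduled assessments when defining baseline, so the two ends of the comparison are treated differently.

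**2. Does any planned summary pick these values up?**

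| Domain | Planned summary | Post-baseline value used |
|---|---|---|
| Laboratory (18.3) | By visit; shift from screening | Nominal visit; not named for the shift |
| ECG (18.4) | Descriptive (by visit in protocol 14.5.7) | Not named |
| Vital signs (18.5) | Values and changes by visit | Nominal visit |
| Examination (18.6) | By visit, with shift from baseline | Not named beyond the visit |

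No row specifies a worst or last post-baseline value.

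**3. An early leaver assessed on Day 20, under each rule.**
- Nominal visit (6.3): the assessment is recorded as Visit 3 and enters the Week 8 column, unmarked, after 19 days on the combination.
- Visit windows (6.4): Day 20 lies in the unassigned stretch from Day 3 to Day 52, which is 52 - 3 + 1 = 50 days, so the value has no column.

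The SAP does not say which rule governs. Table A also does not match the permitted visit window. By SAP 6.1 the first dose is Day 1, so Week 8 is Day 56 + 1 = 57, and the allowed ±3 days run from Day 54 to Day 60. Table A ends at Day 59.

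**4. How many patients leave early?** The only attrition figure is 25%, covering Visit 1 to Visit 3. It reproduces the screening number: 216 / (1 - 0.25) = 288, against 290 stated. No rate is given for the combination period alone. Protocol section 7 caps entry at 110 per run-in drug, so 2 × 110 = 220 can start the combination.
- If 216 complete: 220 - 216 = 4, or 4/220 = 1.8%.
- If 5 to 15% stop early (assumed): 0.05 × 220 = 11 to 0.15 × 220 = 33.
- If the whole 25% fell after Visit 2: 0.25 × 220 = 55. That leaves 165 completers, well short of 216, so it is a ceiling and not an expectation.

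These counts are early leavers. The documents give no basis for counting unscheduled tests in patients who complete.

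**The case against.** The strongest counter-argument is that harms are tabulated elsewhere. SAP 18.1 and 18.2 plan tables of all treatment-emergent events, serious events, events leading to discontinuation, fatal events and deaths. None is by visit, so 6.3 does not restrict them. Protocol 11.9 requires laboratory abnormalities that the investigator considers clinically relevant to be reported as adverse events, and protocol 10.2.1 does the same for new or worsened examination findings. This stands to a large extent: the patients and many of their harms remain in the summaries. It does not close the gap, because reporting a laboratory value as an event rests on judgement, and the parameter tables are the independent numerical check. In addition, SAP 18.1.2 identifies discontinuation events by a recorded stop reason of adverse event, while protocol section 12 lists abnormal renal or liver values as a separate withdrawal reason. A withdrawal under the laboratory rule could therefore be missing from that table.

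A second objection is that SAP section 8 refers to output templates, which are not among the documents available here and might contain further tables. That is fair, and the point is limited to the SAP text.

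A third is that patients also leave by request, through non-compliance or through loss to follow-up, so early leavers need not have worse values. This also stands. The expected direction of bias rests on unscheduled tests being prompted by concern, not on early leaving as such.

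Finally, this is a Phase IV study of two marketed products, every measurement is listed, and the plan breaks no stated commitment. That bears on how serious the point is, not on whether the summaries are incomplete.

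**Conclusion.** The point holds in limited form. Unscheduled values are explicitly kept out of by-visit summaries, the SAP text specifies no worst or last post-baseline summary, and the schedule has no intermediate visit to capture such values. The parameter summaries therefore lean towards a safer picture. Separately, SAP 6.3 and 6.4 give different results for an early Visit 3 assessment.

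The number of early leavers is about 4, 11 to 33, or at most 55 of 220, depending on an attrition rate that the documents do not state. The size of any bias cannot be calculated.

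Three stronger readings are tempting and not supported:
- A reader might infer that early-discontinuation and retest data are barred from the summaries. The SAP says only that listings will include them; the exclusion is stated for unscheduled measurements alone.
- A reader might infer that the safety tables describe completers only. Early leavers in the safety population still contribute to the Visit 1 and Visit 2 columns, and at most the Week 8 results are affected, under the window reading. Patients who stopped because of harm are also not lost from the adverse-event tables.
- A reader might want to show an abnormality rate of zero in the Week 8 table against a positive rate in all collected data. The SAP text plans no table of threshold exceedances, and the counts would be invented.

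This is an inexpensive improvement worth making, not a flaw that invalidates the safety analysis.

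**What to change.** Keep the by-visit tables. In SAP 6.3 and 6.4, state whether the nominal visit or Table A governs an early-termination assessment.

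In SAP 18.3 to 18.5, add for each laboratory, ECG and vital-sign parameter a summary of the worst and of the last post-baseline value. Use all scheduled, unscheduled, retest and early-termination measurements after the first combination dose. Base the laboratory and physical-examination shift tables (18.3, 18.6) on the worst post-baseline result, with safety-population patients who have any post-baseline value as the denominator. These additions work under either reading of the visit rule.

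The cost is SAP wording and a few extra tables from data already collected, with no change for sites or patients. The drawback is that patients who were retested contribute more readings, so their worst value tends to be more extreme by chance. The last-value summary, read beside it, helps to put that in proportion.
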